### **9.2.1 Screening Period: Visit 1 (Days -28 to -7) and Visit 2 (Days -14 to -1, Baseline)**

The first screening visit will occur within -28 to -7 days prior to Day 0. The following procedures will be performed:

- Informed consent
- Demographics data collection: date of birth, country, gender, and ethnicity
- Physical examination (including weight and height for body mass index [BMI])
- All current and past medical conditions and disease history
- Verification of inclusion and exclusion criteria
- Vital signs (pulse, blood pressure, and body temperature) measurements
- 12-lead ECG
- Serology for HIV, and Hepatitis B and C
- Hematology assessments: complete blood count (CBC) with differential, activated partial prothrombin time (aPTT), prothrombin time (PT), and international normalization ratio (INR)
- Serum chemistry
- Urinalysis
- Serum sample for pregnancy test
- Recording of AEs and concomitant medications
- Stool sample for *C. difficile*, culture, and calprotectin
- Distribution of diary

The second screening (baseline) visit will occur within -14 to -1 days prior to Day 0.

The following procedures will be performed:

- Verification of inclusion and exclusion criteria

- Vital signs (pulse, blood pressure, and body temperature) measurements
- Recording of AEs and concomitant medications
- UCDAI
- Flexible sigmoidoscopy
- Distribution of diary

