#### AE Reporting

Patients will be instructed to report AEs at each study visit. All AEs are to be followed until resolution or until a stable clinical endpoint is reached.

Each AE is to be documented on the CRF with reference to date of onset, duration, frequency, severity, relationship to study drug, action taken with study drug, treatment of event, and outcome. Furthermore, each AE is to be classified as being serious or non-serious. Changes in AEs and resolution dates are to be documented on the eCRF.

For the purposes of this study, the period of observation for collection of AEs extends from the time the patient gives informed consent until the follow-up visit (Visit 7). Follow-up of the AE, even after the date of therapy discontinuation, is required until the event resolves or stabilizes at a level acceptable to the Investigator.

Specific guidelines for classifying AEs by intensity and relationship to study drug are given in Table 4 and Table 5.

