### 7.9.1 Adverse Events

All reported Adverse Event (AE) verbatim terms will be coded using the MedDRA dictionary version 17.0 or higher to provide the body system and preferred term.

A TEAE is defined as an adverse event that starts on or after the date of first dose of study medication. If the start date of an adverse event is incomplete or missing, the event will be assumed to be a TEAE, unless the incomplete start date (month and/or year) or the stop date (complete or incomplete) clearly indicates that the event started prior to dosing. Duration of the AE will be calculated in days as (AE stop date – AE start date) + 1, and will be calculated only for those events with both a complete start and stop date.

The relationship of each AE to study drug will be recorded as unrelated, unlikely, possibly, probably, and definitely. If a relation is missing for an AE, the relation of the event to study drug will conservatively be assumed to be definitely for summarization.

The severity of each AE will be classified as mild, moderate, or severe. If the severity of an AE is missing, the severity of the event will conservatively be assumed to be severe for summarization.

Number of events (e), number of patients (n) having an event, and percentage of safety patients (%) having an event will be presented by treatment group and overall for all AE and TEAE summary tables.

An overall summary of AEs and TEAEs will summarize the number of events, and the number and percentage of patients with events by treatment group and overall for the safety population.

The following categories will be included in this overall summary:

- at least one AE
- at least one related AE
- at least one SAE

- at least one related SAE
- at least one severe AE
- at least one TEAE
- at least one TEAE leading to discontinuation of study drug
- at least one related TEAE
- at least one related TEAE leading to discontinuation of study drug
- at least one serious TEAE
- at least one related serious TEAE
- at least one severe TEAE
- at least one related severe TEAE

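### SAP 7.9.1 turns a missing causality into a definite drug relationship even for adverse events that began before the first dose

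*SAP*

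**What the plan says.** SAP 7.9.1 gives the rule for a blank causality field: "If a relation is missing for an AE, the relation of the event to study drug will conservatively be assumed to be definitely". It applies to any AE. SAP Section 10 refers back to 7.9.1 for missing AE data and adds no restriction.

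The same section defines the narrower set: "A TEAE is defined as an adverse event that starts on or after the date of first dose of study medication". The summary table covers both sets: "An overall summary of AEs and TEAEs will summarize the number of events, and the number and percentage of patients with events by treatment group". Its rows include one for related AEs and one for "at least one related SAE". Separate rows follow for related TEAEs and related serious TEAEs.

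On collection, Protocol 11.8.1 (AE Reporting) states that "the period of observation for collection of AEs extends from the time the patient gives informed consent until the follow-up visit". Protocol 9.2.1 lists "Recording of AEs and concomitant medications" among the procedures at both screening visits. Causality is a field for every event: "Each AE is to be documented on the CRF with reference to date of onset, duration, frequency, severity, relationship to study drug".

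**The concern.** An event that began before the first dose cannot have been caused by study drug. The usual argument for imputing the worst category is that the truth is unknown and the analysis should err towards caution. Here the onset date settles the question, so the imputed value is wrong rather than cautious.

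Nor does the error have a fixed direction. A spurious related event can fall in either dose group or in placebo. In an active arm it makes that dose look worse; in placebo it makes the active arms look better by comparison. With 17 patients planned per arm, one patient is a visible step in a percentage.

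**Working it through.** The SAP states no figure to reproduce. The check sets the provisions side by side and then sizes the effect.

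**Does the rule reach events before the first dose?**

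1. AEs are recorded from consent, including at Visits 1 and 2 (Protocol 9.2.1, 11.8.1 and Table 2). Dosing follows randomization at Visit 3.
2. A TEAE must start on or after the first-dose date (SAP 7.9.1). The AE rows are therefore the wider set and include screening events.
3. The missing-causality rule covers any AE, and SAP Section 10 does not narrow it.
4. The safety population (SAP Section 4) drops patients who were never dosed. It keeps the earlier events of those who were.
5. SAP 7.9.1 does not list which causality categories count as related, but any sensible grouping includes the definite one.

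A dosed patient's pre-dose event with a blank relationship is therefore counted in the related-AE row, and in the related-SAE row if serious.

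**Is the imputed category possible for such an event?** Protocol Table 5 allows the definite category only when all of its criteria are met. The first is a plausible time sequence after the drug was given. An event before the first dose fails it.

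**Does the SAP recognise this limit elsewhere?** Yes. For incomplete start dates, 7.9.1 assumes an event is treatment-emergent except where the available dates clearly place its onset before dosing. The causality rule that follows has no such exception.

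**How far does the effect spread?** The tables by system organ class and preferred term, including those by relationship and severity, use TEAEs only. An event dated before the first-dose date enters none of them.

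**Size.** Inputs: 17 patients planned per arm and 51 in total (SAP Section 3), assuming all are dosed. For one dosed patient with one such event:

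| Patient's other events | Related-AE row, patients | Related-AE row, events | Related-TEAE row |
|---|---|---|---|
| No other related AE | +1 | +1 | no change |
| Another related AE | no change | +1 | no change from this event |

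In the first case the arm's percentage moves by 1/17 = 0.0588, or 5.9 percentage points, and the overall column by 1/51 = 0.0196, or 2.0 points. If fewer patients are dosed, each step is slightly larger. For the related-SAE row the same holds, with another related SAE as the deciding condition. Under the fix below, each such event adds 0 to both rows.

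**The case against.** The strongest reply is that the rule may hardly ever operate. Protocol 11.8.1 asks for a relationship on each AE. Table 5 offers an unrelated category that suits a screening event. Protocol 13.2 treats an eCRF as complete only once missing data have been resolved. A blank is thus a query to close, and the imputation is a fallback for what remains. This stands as an argument about frequency. It does not make the rule right for the blanks that do remain.

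Second, the consequences are limited. The rows are descriptive, and no hypothesis test or efficacy endpoint uses them. All AEs are listed, so each such event can be traced. The related-TEAE rows are in the same table, so a gap would be visible. This also stands. A gap between AE and TEAE rows is not a fault in itself, since the first set contains the second by design; the fault is only in that part of the gap created by the imputation.

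A reader might go further and infer that blanks are typical before dosing, because there is no drug yet to relate the event to. That is plausible, but nothing in the documents says so. A reader might also take 5.9 points as the effect of every affected patient. The rows count patients with at least one related event, so that figure applies only to a patient who has no other.

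**Conclusion.** The rule is wrong as written, and the point is minor. Followed literally, SAP 7.9.1 assigns pre-dose events with a blank relationship to a category that Protocol Table 5 rules out for them, and reports them as drug-related in two rows of the overall summary.

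The effect on the related-AE row is 5.9 percentage points in an arm per affected patient with no other related AE, assuming 17 dosed patients; otherwise only the event count changes. How many patients would be affected cannot be estimated from the documents, and the data-completeness requirements suggest few.

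The documents do not support reading this as a general inflation of the safety results, because the TEAE tables are unaffected by events dated before the first-dose date. Nor do they support removing the two rows, which are sound once the imputation is limited.

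The companion rule, which sets a missing severity to severe, also has no timing limit. It is not the same error: a screening event can be severe, but it cannot be caused by a drug not yet taken.

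**What to change.** In SAP 7.9.1, restrict the missing-causality imputation to TEAEs. Add that an AE which clearly began before the first dose is counted as unrelated to study drug when its relationship is missing. The word clearly should carry the same meaning as in the SAP's exception for incomplete start dates, so that an event of uncertain onset is still handled cautiously. Keep the related-AE and related-SAE rows.

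One residual case should be noted. The TEAE definition uses the date of first dose, not the time, so an event earlier on the dosing day remains treatment-emergent and would still take the imputed value if its relationship is blank. Onset dates alone cannot separate such events.

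The cost is a sentence or two in the SAP and one condition in the table program. Data collection and trial conduct do not change.

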### **7.9.2 Physical examinations**

The number of safety population patients reporting normal, abnormal not clinically significant (NCS), abnormal clinically significant (CS), or not examined results for physical examination will be tabulated for each body system at baseline (the last assessment prior to the first dose of study drug), Visit 3, Visit 6, and Visit 7 (follow-up) using counts and percentages, by treatment group and overall.

Physical examination results will also be listed.

### **7.9.3 Vital Signs**

Descriptive statistics will be used to summarize vital signs (body temperature, heart rate, sitting systolic blood pressure, sitting diastolic blood pressure, respiration rate, and body weight) and weight for each treatment group and overall by scheduled study visits. Values and change from baseline values for each visit (change from baseline = post baseline visit value – baseline [last value collected prior to first dose of study drug] value) will be summarized for the safety population.

The number and percentage of patients with result classified as abnormal CS and abnormal NCS will be summarized by treatment group and overall at each visit.

All vital sign data will be listed.

#### 7.9.4 Laboratory Evaluations

The following tests will be performed throughout the study for hematology, serum chemistry, coagulation, and urinalysis:

Hematology	Serum chemistry	Coagulation	Urinalysis (dipstick)
Full and differential blood count	Albumin	Prothrombin time (PT)	Appearance
Hematocrit (Hct)	Alanine aminotransferase (ALT)	Activated partial thromboplastin time (PTT)	pH
Hemoglobin (Hb)	Alkaline phosphatase (ALP)		Protein
Mean corpuscular hemoglobin (MCH)	Aspartate aminotransferase (AST)		Glucose
Mean corpuscular hemoglobin concentration (MCHC)	Blood urea nitrogen (BUN) or Urea	INR (international normalization ratio)	Ketone bodies
Mean corpuscular volume (MCV)	Creatinine		Indicators of blood
Platelet count	Creatine phosphokinase (CPK)		Indicators of WBC
Red blood cell (RBC) count	Electrolytes (Na, K,)		Specific gravity
White blood cell (WBC) count with differential	Gamma-glutamyl transpeptidase (GGT)		Urobilinogen
	Glucose		
	Lactate dehydrogenase (LDH)		
	Total bilirubin		
	Total cholesterol		
	Triglyceride		
	C-reactive protein (CRP)		

Descriptive statistics will be presented for quantitative laboratory parameters by treatment group and time point. Baseline will be the last value collected prior to the first dose of study drug. Changes from baseline (change from baseline = post baseline visit value – baseline visit value) will also be summarized by descriptive statistics where only patients with observations at both baseline and any given visit are included. Number and percentage of patients will be presented

for categorical laboratory parameters by treatment group and time point. Shift analysis will not be performed for categorical laboratory parameters.

Shifts in laboratory test values will be presented in terms of number and percent of patients at each post-baseline visit with a result of low, normal, high, or missing (relative to the normal range for the given parameter) relative to their result at baseline classified as low, normal, high, or missing. Summarization will be by treatment group.

Patients with an incidence of clinically significant abnormalities that occur during treatment as well as those that occur prior to the start of the study treatment but worsened during the study treatment will be listed by treatment group.

All laboratory data will be listed with clinically relevant values flagged (L=Lower than normal range, H=Higher than normal range, or A=Abnormal if no reference range).

A listing of abnormal laboratory values as identified by the investigator on the case report form will be presented with clinical significance status.

Serum and urine pregnancy test results will be listed.

#### **7.9.5 12- Lead Electrocardiogram Evaluation**

12-lead electrocardiograms are performed at Visit 1 (screening) and Visit 6 or early termination; Visit 1 results (the last assessment prior to the first dose of study drug) will be used as baseline. The number and percentage of safety population patients with normal, abnormal not clinically significant (NCS), and abnormal clinically significant (CS) results will be summarized at Visit 1 (screening) and Visit 6.

Shift tables will be presented at Visit 6 showing the number and percentage of safety population patients per treatment group with normal, abnormal NCS, and abnormal CS, and missing at baseline versus Visit 6 results.

All ECG results will be listed.

#### **7.9.6 Death**

All death data will be listed.

## **8. PK/PD ANALYSIS**

Not applicable to this SAP.

## **9. ANALYSIS OF OTHER ASSESSMENTS**

Not applicable to this SAP.

## **10. HANDLING OF MISSING VALUES AND OUTLIERS**

A non-responder imputation approach will be used for the primary efficacy endpoint data (see details in Section 7.8.1 of this SAP). No imputation will be done for secondary and exploratory endpoints. Missing data handling approaches for AE are in Section 7.9.1.

## **11. POOLING OF INVESTIGATIVE SITES**

Not applicable to this SAP.

## **12. INTERIM ANALYSIS**

No interim analysis is planned.

## **13. DATA MONITORING COMMITTEE**

Not applicable to this SAP.

## **14. CHANGES FROM ANALYSIS METHODS PLANNED IN THE PROTOCOL**

Any changes to planned analyses, if applicable, will be cited in the clinical study report along with the rationale for the change.

## **15. STATISTICAL SOFTWARE**

All statistical analyses will be performed using Statistical Analysis System (SAS®) release 9.4 or higher.

## 17. APPENDIX

### 17.1 Modified Ulcerative Colitis-Disease Activity Index Scoring System

	Mild (score = 1)	Moderate (score = 2)	Severe (score = 3)
Rectal bleeding	Streaks of blood	Obvious blood	Mostly blood
Stool frequency	1-2/day > normal	3-4/day > normal	>4/day > normal
Mucosal appearance	Erythema Decreased vascular pattern Minimal granularity	Marked erythema Friability Granularity Absent vascular pattern Bleeding minimal trauma No ulcerations	Ulceration Spontaneous bleeding
Physician's Global Assessment	Mild	Moderate	Severe

Note: Normal = 0

Modified from Sutherland et al. (Mucosal friability moved from a score of 1 to 2).

Note: In those cases, when patients have variable values for one or more modified UCDAI items, the average must be calculated.

### 17.2 Inflammatory Bowel Disease Questionnaire (IBDQ)

Not done

Date of completion: \_\_\_\_\_ (DD-MMM-YYYY)

✓ Please Tick only one option per question listed below

#### 1. How frequent have your bowel movements been during the last 2 weeks?

- Bowel movements as or more frequent than they have ever been
- Extremely frequent
- Very frequent
- Moderate increase in frequency of bowel movements
- Some increase in frequency of bowel movements
- Slight increase in frequency of bowel movements
- Normal, no increase in frequency of bowel movements

#### 2. How often has the feeling of fatigue or being tired and worn out been a problem for you during the last 2 weeks?

- All of the time

- Most of the time
- A good bit of the time
- Some of the time
- A little of the time
- Hardly any of the time
- None of the time

**3. How often during the last 2 weeks have you felt frustrated, impatient, or restless?**

- All of the time
- Most of the time
- A good bit of the time
- Some of the time
- A little of the time
- Hardly any of the time
- None of the time

**4. How often during the last 2 weeks have you been unable to attend school or work because of your bowel problem?**

- All of the time
- Most of the time
- A good bit of the time
- Some of the time
- A little of the time
- Hardly any of the time
- None of the time

**5. How much of the time during the last 2 weeks have your bowel movements been loose?**

- All of the time
- Most of the time
- A good bit of the time
- Some of the time
- A little of the time
- Hardly any of the time
- None of the time

**6. How much energy have you had during the last 2 weeks?**

- No energy at all

- Very little energy
- A little energy
- Some energy
- A moderate amount of energy
- A lot of energy
- Full of energy

**7. How often during the last 2 weeks did you feel worried about the possibility of needing to have surgery because of your bowel problem?**

- All of the time
- Most of the time
- A good bit of the time
- Some of the time
- A little of the time
- Hardly any of the time
- None of the time

**8. How often during the last 2 weeks have you had to delay or cancel a social engagement because of your bowel problem?**

- All of the time
- Most of the time
- A good bit of the time
- Some of the time
- A little of the time
- Hardly any of the time
- None of the time

**9. How often in the past 2 weeks have you been troubled by cramps in your abdomen?**

- All of the time
- Most of the time
- A good bit of the time
- Some of the time
- A little of the time
- Hardly any of the time
- None of the time

**10. How often during the last 2 weeks have you felt generally unwell?**

- All of the time
- Most of the time
- A good bit of the time
- Some of the time
- A little of the time
- Hardly any of the time
- None of the time

**11. How often during the last 2 weeks have you been troubled because of fear of not finding a bathroom?**

- All of the time
- Most of the time
- A good bit of the time
- Some of the time
- A little of the time
- Hardly any of the time
- None of the time

**12. How much difficulty have you had, as a result of your bowel problems, doing leisure or sports activities you would have liked to have done during the last 2 weeks?**

- A great deal of difficulty; activities made impossible
- A lot of difficulty
- A fair bit of difficulty
- Some difficulty
- A little difficulty
- Hardly any difficulty
- No difficulty; no limit sports or leisure activities

**13. How often during the last 2 weeks have you been troubled by pain in the abdomen?**

- All of the time
- Most of the time
- A good bit of the time
- Some of the time
- A little of the time
- Hardly any of the time
- None of the time

**14. How often during the past 2 weeks have you had problems getting a good night's sleep, or been troubled by waking up during the night?**

- All of the time
- Most of the time
- A good bit of the time
- Some of the time
- A little of the time
- Hardly any of the time
- None of the time

**15. How often during the past 2 weeks have you felt depressed or discouraged?**

- All of the time
- Most of the time
- A good bit of the time
- Some of the time
- A little of the time
- Hardly any of the time
- None of the time

**16. How often during the past 2 weeks have you had to avoid attending events where there was no washroom close at hand?**

- All of the time
- Most of the time
- A good bit of the time
- Some of the time
- A little of the time
- Hardly any of the time
- None of the time

**17. Overall, in the past 2 weeks, how much problem have you had with passing large amounts of gas?**

- A major problem
- A big problem
- A significant problem
- Some trouble
- A little trouble
- Hardly any trouble

No trouble

**18. Overall, in the last 2 weeks, how much of a problem have you had maintaining or getting to the weight you would like to be at?**

- A major problem
- A big problem
- A significant problem
- Some trouble
- A little trouble
- Hardly any trouble
- No trouble

**19. Many patients with bowel problems often have worries and anxieties related to their illness. These include worries about getting cancer, worries about never feeling better, and worries about having a relapse. In general, how often during the last 2 weeks have you felt worried or anxious?**

- All of the time
- Most of the time
- A good bit of the time
- Some of the time
- A little of the time
- Hardly any of the time
- None of the time

